9.10 Scoring of HRQOL Data

Unless otherwise specified, HRQOL questionnaires will be scored using their published administration and scoring manual. For items with missing responses, the response will be managed as per the scoring manual. See Section 14.2.7 for details.

9.11 Tumor Evaluation and Adjudication

Missing data from scheduled tumor assessments not performed will not be imputed. Evaluable tumor assessments are defined as those with an overall response of CR, PR, SD or PD. Data from non-evaluable (NE) tumor assessments will be used in the derivation of endpoints in accordance with Eisenhauer et al., 2009.

For IRC assessments, only the response assessments which are flagged as accepted after adjudication will be taken over to ADaM datasets and will be analyzed. In the case of a missing adjudication flag for a response assessment and the earliest image dates being equal, the assessment of reader 1 (the reader who completed baseline first) will be taken for analysis. Otherwise the assessment for the reviewer who reviewed the record with the earliest image date will be analyzed. Analyses of tumor sizes will be based only on assessments of the reader whose assessment was accepted at baseline.

For those participants in the monotherapy arm who switch to combination treatment, the latest available scan at the time of switch will be used to perform the baseline tumor assessment for the combination period. Only investigator assessments will continue after the switch and data will be collected in the usual eCRF pages dedicated to collection of tumor response. These evaluations will be called "Evaluation re-baseline", "Evaluation after re-baseline visit 1", etc. IRC assessments will stop at the first PD.

10 Study Participants

The subsections in this section include specifications for reporting participant disposition and study treatment/study discontinuations. Additionally, procedures for reporting protocol deviations are provided.

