9.4 Statistical Analyses

Details of the statistical analyses will be described in a separate IAP.

Continuous variables will be summarized using descriptive statistics, ie, number of participants with non-missing values (n), mean, median, standard deviation, 2-sided 95% CIs where appropriate, 25th and 75th percentiles, minimum, and maximum.

Qualitative variables and rates will be summarized by counts and percentages along with 2-sided exact Clopper-Pearson 95% CIs. Unless otherwise stated, the calculation of proportions will be based on the sample size of the analysis set of interest. Counts of missing observations will be included in the denominator and presented as a separate category.

In general, the last measurement prior to first administration of study intervention will serve as the baseline measurement.

In order to provide overall estimates of the treatment effects, data will be pooled across sites. The factor site will not be considered in statistical models or for subgroup analyses because of the high number of participating sites and the anticipated small number of participants enrolled at each site.

The independent review will be performed by an IRC which will conduct an independent review of the tumor assessment images of all participants using the same criteria based on a separate charter outlining details of the review process.

Non-compartmental computation as well as descriptive statistical analyses of PK parameters will be performed using the software Phoenix® WinNonlin® 6.3 or higher (Certara, L.P., Princeton, New Jersey) or equivalent software. All other statistical analyses will be performed using SAS® Version 9.2 or higher.

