14.1 Primary Endpoint: Objective Response by IRC

14.1.1 Derivation and analysis

BOR will be assessed based on reported overall responses at different evaluation time points from the study treatment start date until documented disease progression in accordance with RECIST v1.1, taking requirements for confirmation into account as detailed below. Clinical deterioration will not be considered as documented disease progression. The date of the overall response assessment is the earliest date for imaging of target, non-target and new lesions of images taken at that response assessment.

BOR Based on Confirmed Responses:

- CR = at least two determinations of CR at least 4 weeks (28 days) apart (with no PD in between)
- PR = at least two determinations of PR or better (PR followed by PR or PR followed by CR) at least 4 weeks (28 days) apart (and not qualifying for a CR), with no PD in between
- SD = at least one SD assessment (or better) ≥ 12 weeks (84 days) after the start date of study treatment (and not qualifying for CR or PR)
- $PD = PD \le 90$ days after start date of study treatment (and not qualifying for CR, PR or SD)
- Not Evaluable (NE): all other cases.

There may be uncommon situations where the above rules might need further explanation. Some of these cases are listed below together with the BOR value that should be assigned:

- SD can follow PR only in the rare case that tumor increases by less than 20% from the nadir, but enough that a previously documented 30% decrease from baseline no longer holds. If this occurs, the sequence PR-SD-PR is considered a confirmed PR. A sequence of PR-SD-SD-PD would be a best response of SD if the minimum duration for SD definition has been met.
- When an unconfirmed PR or CR is assessed at least 12 weeks after the start date of study treatment with no PD before, the best response would be SD.
- When there is an assessment of SD, PR or CR within 12 weeks from the start of study treatment followed by a PD after 90 days, the best response would be NE.

Participants are defined as having an Objective Response (OR) if they achieved either a confirmed BOR of CR or PR according to RECIST v1.1 from first administration of study treatment to first observation of PD.

The OR rate (ORR) is the proportion of participants with OR in the analysis set.

No formal statistical hypotheses will be tested.

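### Where the adjudication flag is missing, SAP 9.11 chooses the IRC reader one assessment at a time, so the confirmed response behind the primary endpoint can mix two readers

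*SAP*

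**What the plan says.** SAP 9.11 sets the main rule for IRC data: "only the response assessments which are flagged as accepted after adjudication will be taken over to ADaM datasets and will be analyzed". A fallback with two branches follows.

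- Equal dates: "In the case of a missing adjudication flag for a response assessment and the earliest image dates being equal, the assessment of reader 1" is taken. Reader 1 is the one who finished the baseline read first, so this reader is fixed for a participant.
- Different dates: "Otherwise the assessment for the reviewer who reviewed the record with the earliest image date will be analyzed".

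For tumour measurements the same section holds to one reader: "Analyses of tumor sizes will be based only on assessments of the reader whose assessment was accepted at baseline".

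SAP 14.1.1 derives the primary endpoint from the resulting series: "BOR will be assessed based on reported overall responses at different evaluation time points". A confirmed PR needs "at least two determinations of PR or better (PR followed by PR or PR followed by CR) at least 4 weeks (28 days) apart". An intervening SD is allowed: "the sequence PR-SD-PR is considered a confirmed PR". None of these sentences says that the two determinations must come from the same reader.

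Protocol 9.4 leaves the conduct of the independent review to another document, as it is "based on a separate charter outlining details of the review process". That charter is not among the documents.

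**The concern.** The fallback is worded for a single response assessment and does not look at which reader supplied the participant's other visits. A series can therefore change reader by two routes:

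- Flags are missing at several visits, and the readers' earliest image dates are equal at some visits and different at others, or differ in opposite directions.
- One visit is flagged as accepted for reader 2, and an unflagged visit with equal dates defaults to reader 1.

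Different earliest dates are possible in principle, because SAP 9.9 (tumor assessments) provides for scans of one evaluation that are spread over several days.

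Protocol Appendix 7 gives the purpose of confirmation: to guard against responses that are only measurement error. Two isolated PR calls, one from each reader, do not serve that purpose if each reader's own next read contradicts the call. The primary endpoint is at stake, and so are the IRC versions of duration of response, disease control and PFS (SAP 14.2.3 to 14.2.5), which use the same reads. In the waterfall plot of SAP 14.1.1, the bar follows the tumour-size reader and the BOR colour follows the response rule, so the two can come from different readers.

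**Working it through.** **Inputs.** Reader rule: SAP 9.11. Confirmation rule: SAP 14.1.1. Assessment interval: 6 weeks ± 7 days during the first 9 months (protocol 8.1), so consecutive assessments are at least 42 − 14 = 28 days apart and can confirm each other. Planning figures: n = 80, true ORR 50%, reference 35%, exact two-sided 95% interval, stated probability 78% (protocol 9.2).

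**The plan's own figure.** The smallest count out of 80 with a Clopper-Pearson lower limit above 35% is 37 (interval 35.03% to 57.76%). P(X ≥ 37 | n = 80, p = 0.50) = 0.783, which reproduces the 78%.

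**Can a response be created?**

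| | Visit 1 | Visit 2 | Visit 3 | Confirmed? |
|---|---|---|---|---|
| Reader 1 | PR | SD | SD | no |
| Reader 2 | SD | PR | SD | no |
| Analysed: reader 1, then 2, then either | PR | PR | SD | yes |

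This needs unflagged visits with equal dates (or an earlier date for reader 1) at visit 1 and an earlier date for reader 2 at visit 2. The PR-SD-PR allowance adds further cases: PR-SD-SD and SD-SD-PR, read by reader 1 at visit 1 and reader 2 at visit 3, give PR-SD-PR.

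**Can a response be lost?** Let reader 1 record PR-PR-SD and reader 2 record SD-PR-PR. Both are confirmed. Taking reader 2 at visit 1 and reader 1 at visit 3 gives SD-PR-SD, which is not confirmed.

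**Enumeration.** Take three visits with SD, PR or PD, where PD is final once recorded.

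- Possible sequences per reader: 8 without PD + 4 with first PD at visit 3 + 2 at visit 2 + 1 at visit 1 = 15.
- Pairs of readers: 15 × 15 = 225.
- Ways to pick a reader at each visit that use both readers: 2³ − 2 = 6.
- Mixed patterns: 225 × 6 = 1350.
- Neither reader confirms, but the analysed series does: 42.
- Both readers confirm, but the analysed series does not: 20.
- One reader fixed for all visits: 0 of either kind, because the analysed series is then that reader's own.
- Flags missing throughout and dates equal at every visit: 0, because reader 1 is always used.

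These are counts of patterns, not probabilities. They show that both errors are possible and say nothing about how often either occurs.

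**Size per participant.** 1/80 = 1.25 percentage points of ORR. As a scale for the interval, 36/80 has a lower limit of 33.85% and 37/80 has 35.03%, a step of 1.18 points.

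**The case against.** The strongest reply is that this is a residual rule. Adjudicated reads are analysed first, and the fallback acts only where a flag is absent. When adjudication is triggered, whether acceptance is given per participant or per time point, and why a flag might be missing are all matters for the charter. If image dates agree, the fallback fixes reader 1 and no mixing arises from unflagged visits alone. All of this stands, and it limits the point to a gap of unknown use.

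Three stronger readings are tempting and are not supported:

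- **The ORR is inflated.** The error runs both ways, and the pattern counts carry no weights, so no upward bias follows.
- **One participant can decide the trial.** Protocol 9.1 and SAP 14.1.1 test no formal hypothesis. The 35% bound appears only in the sample-size text, with no success rule attached.
- **The image-date rule pulls response and progression dates forward.** The earliest scan date is the SAP's general convention for dating an assessment (9.9 and 14.1.1). An earlier response date lengthens duration of response and an earlier progression date shortens it, so no net effect is shown.

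It can also be said that each time-point response is judged against that reader's own baseline, and that Appendix 7 sets no same-reader condition. That is true of each single read, but it does not make two contradictory readers a confirmation.

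The other safeguards do not close the gap. Investigator-assessed ORR (14.2.1) and the IRC-versus-investigator concordance table (14.1.3) do not compare the IRC readers with each other. Data review before lock (6.3) might find missing flags, but it does not change the rule.

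**Conclusion.** The gap holds as a matter of wording. Followed literally, the missing-flag rule in SAP 9.11 can assemble a confirmed response that neither IRC reader recorded, or lose one that both recorded, and nothing in SAP 14.1.1 prevents this. It also departs from the one-reader rule that the same section applies to tumour sizes.

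The size is 1.25 points of ORR per affected participant at n = 80. The number affected and the net direction cannot be derived from the documents. They depend on the IRC charter, on how many flags are missing and on how often the readers' earliest image dates differ. If no flag is missing, the effect is nil. This is an inexpensive clarification of how the primary endpoint is derived, not evidence that the reported ORR will be wrong.

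**What to change.** In SAP 9.11:

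1. Keep every response assessment flagged as accepted after adjudication; the change must not override those reads.
2. For unflagged assessments, replace the image-date rule with one reader per participant: the reader accepted at baseline, as already used for tumour sizes, or reader 1 at all visits if the participant has no flag at all.
3. Report how many assessments and how many participants used the fallback.
4. Add, as a sensitivity analysis, ORR from each IRC reader's complete sequence.

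This removes mixing among unflagged visits. If the charter lets adjudication accept different readers at different time points, that mixing remains; the SAP should then say so, and item 4 shows its effect.

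The cost is a few sentences, a small change to the ADaM record selection and one extra table. Sample size, interval method and planning probability do not change. If the primary analysis has already been run, the rule and the counts can still be applied to the analysis after the Chinese extension period (SAP 6.4) and the final analysis (SAP 6.5).

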10.1 Disposition of Participants and Discontinuations

All participants who performed prescreening will be considered. Percentages will be presented with respect to the number of SAF Analysis Set participants. Results will be presented as indicated in Sections 8.1.1 and 8.1.2.

Participant disposition will be summarized as follows, as applicable:

- Number of participants prescreened
- Number of participants prescreened based on protocol version 2.0 onwards
- Number of participants screened

Tepotinib (MSC2156119J)Tepotinib plus osimertinib in osimertinib-relapsed MET amplifiedMS200095-0031 (version 4.0)NSCLC

- Number of participants who discontinued from the study prior to first dose of study treatment, overall and grouped by the main reason (e.g., the failed specific inclusion or exclusion criteria, withdrawal of consent)
- Number of participants active in screening (for outputs while recruitment is still ongoing)

The end of treatment status will be summarized by:

- Number of participants who received at least one dose of study treatment
- Number and percentage of participants who have permanently discontinued study treatment
- Number and percentage of participants with study treatment ongoing
- Number and percentage of participants who did not receive tepotinib
- Number and percentage of participants with tepotinib treatment ongoing
- Number and percentage of participants who permanently discontinued tepotinib treatment (overall and by primary reason)
- Number and percentage of participants who did not receive osimertinib
- Number and percentage of participants with osimertinib treatment ongoing
- Number and percentage of participants who permanently discontinued osimertinib treatment (overall and by primary reason)
- Number and percentage of participants in the monotherapy arm who switched to the combination treatment
- Number and percentage of participants in the monotherapy arm who switched to the combination treatment and treatment is still ongoing
- Number and percentage of participants in the monotherapy arm who switched to the combination treatment and treatment is permanently discontinued

The end of study status will be summarized by:

- Number and percentage of participants with any study treatment ongoing
- Number and percentage of participants in the monotherapy arm who switched to the combination treatment and treatment is still ongoing
- Number and percentage of participants off-treatment and in safety or survival follow-up
- Number and percentage of participants who discontinued the study (overall and by primary reason)

For each participant in the SAF analysis set, the first and last dosing date for each study component (including reason for treatment discontinuation) and study discontinuation date (including reason for study discontinuation) will be listed. For participants in the monotherapy arm who switch treatment, the first and last dosing date of each study component (including reason for treatment discontinuation) will also be listed.

Additionally, the number of participants enrolled in each analysis population will be provided overall, by region, by country within region and by site. Results will be presented by treatment arm. This information will also be provided for each participant in the SAF analysis set in a listing.

10.2 MET Amplification Results in Blood and Tissue Samples

The MET amplification result according to the local and central TBx (FISH) as well as LBx tests for all prescreened participants as well as for participants prescreened based on protocol version 2.0 onwards will be summarized. Frequencies and percentages will be calculated for all the different combinations of results from both the blood and tissue samples. Each result from the central liquid and tissue sample will be classified as Positive, Negative, Not Evaluable, Not Analyzed or No Sample Taken whereas the result from the local tissue sample will be classified as Positive, Negative or No Sample Taken.

10.3 Protocol Deviations / Exclusion from Analysis Populations

10.3.1 Important Protocol Deviations

Important protocol deviations (IPDs) are protocol deviations that might significantly affect the completeness, accuracy, and/or reliability of the study data or that might significantly affect a participant's rights, safety, or well-being.

Important protocol deviations include, but are not limited to:

- Participants enrolled and dosed on the study who did not satisfy enrollment criteria
- Participants who are not compliant with treatment: overdose, dose modifications not as per protocol, incorrect dose, etc.
- Participants who receive a prohibited concomitant medication
- Failure to collect data necessary to interpret primary endpoints
- Failure to collect necessary key safety data
- Deviation from Good Clinical Practice (GCP)
- Any other protocol deviation that might significantly affect the completeness, accuracy, and/or reliability of the study data or that might significantly affect a participant's rights, safety, or well-being.

All IPDs are documented in SDTM datasets whether identified for all participants by either medical review processes or programmed by IQVIA Data Management and confirmed prior to or at the Data Review Meeting at the latest.

The protocol deviations recorded in the Clinical Trial Management System (CTMS) may utilize different terminology. The table below displays how the terminology used in CTMS translates to the terminology used in the IAP, the SDTM and ADaM datasets, and ultimately the CSR:

CTMS	IAP	SDTM	ADaM
CONFIDENTIAL 39/94 INFORMATION 39/94			

Minor	Non-important	Millior (all prolocol	Minor (only protocol deviations related to COVID-19 are included)
Major	Important	Flagged with PDEVXXX code	Flagged with PDEVXXX code
Critical (subset of Major)	Important	Mapped to Important	Mapped to Important

Clinically important protocol deviations (CIPDs) are flagged in CTMS after medical review and this information will be available in the SDTM datasets.

A full list of potential IPDs including definition and categorization is maintained by IQVIA in a separate document, the Protocol Deviation Management Plan, which is updated as needed during the course of the study.

A frequency table for the IPDs and one for the CIPDs will be created based on the SAF analysis set; all IPDs will be listed and CIPDs will be flagged. All PDs will be tabulated, including those related to the period after the switch from monotherapy to combination treatment. PDs related to the period after the switch will be flagged in the listings.

A listing containing any violation of inclusion/exclusion criteria at screening will also be produced.

On the 16th May 2022, IQVIA implemented changes to the PD management process and IQVIA CTMS to allow a risk-based approach to protocol deviation and site non-compliance reporting, tracking, trending and oversight. Due to the status of this study when these enhancements were implemented, there are two sets of PD categories used. The old categories will be kept for analysis purposes. The mapping from the new to the old categories is performed via programming in the SDTM datasets DV/SUPPDV in accordance to Table 5 of the Protocol Deviation Management Plan from version 4.0 onwards.

10.3.2 Reasons Leading to the Exclusion from the Per Protocol Analysis Set

Not applicable.

11 Demographics and Other Baseline Characteristics

Demographic data and other baseline characteristics will be presented for the SAF analysis set using summary statistics for continuous variables and frequency statistics (i.e., counts and percentages) for categorical variables. Results will be presented as indicated in Sections 8.1.1 and 8.1.2.

Listings showing demographic data and other baseline characteristics will be presented for the SAF analysis set.

11.1 Demographics

Demographic characteristics will be summarized descriptively using the following information from the Prescreening and Screening/Baseline Visit eCRF pages:

- Sex: male, female
- Race: White, Black or African American, Asian, American Indian or Alaska Native, Native Hawaiian or Other Pacific Islander, not collected at this site, more than one race, other, missing
- Ethnicity:
 - Hispanic or Latino / Not Hispanic or Latino
 - o Japanese / Not Japanese
- Age (years)
- Age categories:
 - < 65 years ≥ 65 years 65 < 7575 < 85
 - \geq 85 years
- Pooled Region: North America, Europe, Asia
- Geographic Region (e.g.: North America, Western Europe, Eastern Europe, Asia, ...)
- Country (e.g.: Belgium, China, Germany, Malaysia, Spain, Turkey, USA, ...)

Specifications for computation:

- Age [years]
 - Age = (date of given informed consent for screening date of birth + 1) / 365.25.

In case of missing day for at least one date, but month and year available for both dates:

the day of informed consent and the day of birth will be set to 1 and the formula above will be used.

In case of missing month for at least one date, but year available for both dates:

the day and the month of informed consent and the day and month of birth will be set to 1 and the formula above will be used.

The integer part of the calculated age will be used for reporting purposes.

• Site codes will be used for the determination of the participant's pooled region, geographic region and country.

• Participants with more than one race will be summarized in the "more than one race" category.

